#### Table 8.

#### b) Demographics and clinical characteristics

Demographics and clinical characteristics that will be assessed in the study include sex, year of birth, medication use (current and prior medications), medical history, height, weight, BMI, vital signs, FVC, ECG, and full physical, neurological, and functional examination. The tests that will be conducted as part of the physical, neurological, and functional examination are part of routine care for participants with *RYR1*-RM and are outlined in Appendix 11.111.1.

All the above demographics and clinical characteristics will be assessed at the Screening Visit. Medication use will also be assessed at Visit 1, Visit 2, and End of Study Visit, and the physical, neurological, and functional examination will be repeated at the End of Study Visit.

## c) Review of symptom diary

A symptom diary will be completed by participants to collect data on their subjective experience of permanent and intermittent symptoms of the disease, as well as medications and other strategies used to manage their symptoms (including healthcare resource utilisation). Participants will record symptoms in the diary on a continuous basis, starting from the Screening Visit until the End of Study Visit.

Template No.: RWI\_TP\_EPI0011 Revision 2 Reference: RWI\_WI\_EPI0005

ARMGO Pharma, Inc. RYR1-RM Study Version 4.0 dated 10-SEP -2024 Protocol/Study No.: CL-EPI-001 Page 36 of 64

## **Table 8 Questionnaires**

Measures	Dimensions	
PROMIS-Fatigue SF v1.0	Frequency of feeling tired	
7a	
 
Frequency of experiencing extreme exhaustion
 
	
	
 
Frequency of running out of energy
 
	
	
 
Frequency of fatigue limiting to work (include work at home)
 
	
	
 
Frequency of feeling too tired to think clearly
 
	
	
 
Frequency of feeling too tired to take a bath or shower
 
	
	
 
Frequency of having enough energy to exercise strenuously
 
	
PROMIS-PF-SF 10a Item	• Being able to dress oneself, including tying shoelaces and doing	
Short Form (Covers Self-	buttons	
care and Lower Extremity)	
 
Being able to shampoo hair
 
	
	
 
Being able to wash and dry body
 
	
	
 
Being able to get on and off the toilet
 
	
	
 
Being able to do chores such as vacuuming or yard work
 
	
	
 
Health limiting in bending, kneeling, or stooping
 
	
	
 
Health limiting in lifting or carrying groceries
 
	
	
 
Health limiting in climbing one flight of stairs
 
	
	
 
Health limiting in walking more than a mile
 
	
	
 
Health limiting in doing vigorous activities
 
	
Additional Item on	
 
Do you have difficulties turning in bed or moving in bed?
 
	
Physical Function		

Template No.: RWI\_TP\_EPI0011 Revision 2 Reference: RWI\_WI\_EPI0005

ARMGO Pharma, Inc. RYR1-RM Study Version 4.0 dated 10-SEP -2024 Protocol/Study No.: CL-EPI-001

Page 37 of 64

Measures	Dimensions
IPAQ 7 Item Short Form	Number of days doing vigorous physical activities like heavy lifting,
(covers past 7 days)	digging, aerobics, or fast bicycling
	Amount of time per day doing those vigorous physical activities
	Number of days doing moderate physical activities like carrying light
	loads, bicycling at a regular pace, or doubles tennis
	Amount of time per day doing those moderate physical activities
	
 
Number of days walking for at least 10 minutes at a time
 

	Amount of time per day spending walking
	Amount of time per day spending sitting

IPAQ, International Physical Activity Questionnaire, PROMIS, Patient-Reported Outcomes Measurement Information System; PROMIS, Patient-Reported Outcomes Measurement Information System; PROMIS-PF, Patient-Reported Outcomes Measurement Information System-Physical Function.

# 4.4.2 Safety Reporting

Any adverse event/serious adverse event (AE/SAE) will be recorded throughout the study. Details of AE/SAE that will be collected are specified in Section 8.

#### 4.4.3 Other Measures

Explorative endpoints include measurements obtained using the Syde® device to objectively assess activity (e.g., stride velocity when walking and climbing stairs) from Screening Visit (Syde® device fitting) to Visit 1 (Syde® device removal).

#### 4.5 Data Sources and Collection

Data will be collected during visits to the site and extracted from the participants' medical records (paper and/or electronic) at the Screening Visit. The data collected at study visits will be manually entered in an eCRF. The relevant data time points for the study are presented in the data collection schedule in

Template No.: RWI\_TP\_EPI0011 Revision 2 Reference: RWI\_WI\_EPI0005

ARMGO Pharma, Inc. RYR1-RM Study Version 4.0 dated 10-SEP -2024 Protocol/Study No.: CL-EPI-001 Page 38 of 64

Table 9. The Screening Visit is anticipated to take approximately 1 hour and 30 minutes, while subsequent visits should take approximately 1 hour.

Template No.: RWI\_TP\_EPI0011 Revision 2 Reference: RWI\_WI\_EPI0005

ARMGO Pharma, Inc. RYR1-RM Study Version 4.0 dated 10-SEP -2024 Protocol/Study No.: CL-EPI-001

Page 39 of 64

#### **Table 9. Data Collection Schedule**

Study Procedure	Screening Visit	Visit 1	Visit 2	End of Study Visit
	(0 day)	(+30 days [±3 days])	(+30 days [- 14/+3 days])	(+30 days [- 14/+3 days])
Informed consent	X	-	-	-
Inclusion/Exclusion	X	-	-	-
Demographics	X	-	-	-
Medical history a	X	-	-	-
Medication use b	X	X	X	X
Strength measurements using QMA, HHD and MMT c	X	X	X	X
10-MWT	X	X	X	X
1-Minute Sit-to-Stand Test	X	X	X	X
4SCT	X	X	X	X
PROMIS Fatigue	X	-	-	X
PROMIS-PF + additional single item	X	-	-	X
IPAQ	X	-	-	X
Vital signs (HR, BP, RR, temperature), FVC, and ECG d	X	-	-	-
Full physical, neurological, and functional examination e	X	-	-	X
Syde® device fitting and removal	X	X	-	
Symptom diary f	X	-	-	X
AE/SAE	X	X	X	X

<sup>a Medical history: Include if a biopsy has been performed and capture related data.

10-MWT, 10-Minute Walk Test; 4SCT, 4 Stair Climb Test; AE, adverse event; BMI, body mass index; BP, blood pressure; ECG, electrocardiogram; FVC, forced vital capacity; HR, heart rate; IPAQ, International Physical Activity questionnaire; PROMIS, Patient-Reported Outcomes Measurement Information System; PROMIS-PF, Patient-Reported Outcomes Measurement Information System-Physical Function; RR, respiratory rate; *RYR1*-RM, Ryanodine receptor isoform 1-related congenital myopathies; SAE, serious adverse event.

Template No.: RWI\_TP\_EPI0011 Revision 2 Reference: RWI\_WI\_EPI0005

<sup>b Medication use: To include all current medication and prior medication to treat symptoms of RYR1-RM.

<sup>c Strength measurements: Shoulder abduction, neck flexion, elbow flexion and extension, knee extension and flexion.

<sup>d Vital signs, FVC and ECG will be assessed at the time of the Screening Visit or based on the most recent assessment captured in the participants' medical records within 12 months prior to the Screening Visit.

<sup>e See list of tests in Appendix 11.1.

f Participants will keep a diary of their symptoms on a continuous basis throughout the study, starting from the Screening Visit up to End of Study Visit.

ARMGO Pharma, Inc. RYR1-RM Study Version 4.0 dated 10-SEP -2024 Protocol/Study No.: CL-EPI-001

Page 40 of 64

# 4.5.1 Screening Visit

The following data will be collected at the Screening Visit for all enrolled participants (listed in the order in which they will be collected during the visit):

- Informed consent;
- Inclusion/Exclusion (including MMT to assess muscle/motor function deficit, 10-MWT to assess ability to walk, and FVC to assess pulmonary dysfunction);
- Demographics (medical records);
- Medical history (medical records);
- Medication use (medical records);
- Vital signs and ECG (medical records or primary data collection; note that FVC will be evaluated as part of the assessment of the exclusion criteria);
- Strength measurements using QMA and HHD (note that MMT will be conducted at the start of the Screening Visit as part of the assessment of the inclusion criteria);
- 1-Minute Sit-to-Stand Test;
- 4SCT:
- Full physical, neurological, and functional examination;
- PROMIS Questionnaires;
- IPAO:
- Syde® device fitting;
- Symptom diary (initiation); and
- AE/SAE.

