## **Documentation of Protocol Amendments**

Date	Section of study protocol	Amendment or update	Reason
December 2023	Exclusion criteria (Section 4.2.2)	Version 2.0	Exclusion criteria have been amended to also exclude pregnant women.
December 2023	Primary Endpoint Measures (Section 4.4.1.1)	Version 2.0	Description of primary endpoint measures has been amended to include more detailed information about the procedures, scoring, and reference values of the tests.
December 2023	Secondary Endpoint Measures (Section 4.4.1.2)	Version 2.0	a) PROMIS Fatigue, PROMIS-PF, and IPAQ questionnaires: Description of questionnaires has been amended to include more information about their scoring and clinical value.
			b) Demographics and clinical characteristics: List of tests performed as part of the physical, neurological, and functional examination has been updated to only include tests that are relevant to the scope of the study and explain how they will be scored.
			c) Diary: It has been clarified that participants will record symptoms into the diary on a continuous basis, starting from the Screening Visit until the End of Study Visit.
December 2023	Data Sources and Collection (4.5)	Version 2.0	The expected duration of the visits has been included.
			The tests have been listed in the order in which they will be administered.
			It has been clarified that Vital signs, FVC and ECG will be assessed at the time of the Screening Visit or based on the most recent assessment captured in the participants' medical records within 12 months prior to the Screening Visit.

Template No.: RWI\_TP\_EPI0011 Revision 2 Reference: RWI\_WI\_EPI0005

ARMGO Pharma, Inc. RYR1-RM Study Version 4.0 dated 10-SEP -2024 Protocol/Study No.: CL-EPI-001

Page 16 of 64

•			1
February 2024	Study Synopsis  Inclusion criteria (4.2.1)	Version 3.0	The inclusion criteria have been amended to include all male and female participants (biological sex*) aged 18 years and older at Screening. A comment has also been included below the inclusion/exclusion criteria stating that biological sex of male or female is required for study inclusion based on the available normative values for the tests conducted, but all gender identities are eligible for inclusion in the study.

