
Template No.: RWI\_TP\_EPI0011 Revision 2 Reference: RWI\_WI\_EPI0005

ARMGO Pharma, Inc. RYR1-RM Study Version 4.0 dated 10-SEP -2024 Protocol/Study No.: CL-EPI-001 Page 19 of 64

functional exercise capacity and quadriceps strength.  $(\underline{12}, \underline{13})$  The Stair Climb Test assesses the ability to climb a flight of stairs and lower extremity strength, power, and balance. (14, 15)

The study also seeks to describe PROs using the Patient-Reported Outcomes Measurement Information System (PROMIS)-Fatigue, PROMIS-Physical Function (PROMIS-PF), International Physical Activity Questionnaire (IPAQ), and symptom diary. Fatigue is one of the most predominant features of chronic illness. In the health outcomes measurement perspective, fatigue is defined as an overwhelming, debilitating, and sustained sense of exhaustion that reduces an individual's ability to carry out daily activities, including the ability to work effectively or function at optimally. (16) It is expected that information on the subjective experience of the participant collected using these PROs would complement the objective assessments conducted using QMA and other muscle strength tests. The PROMIS Fatigue scale will be used as a measure of fatigue severity in this study. Improvements in the PROMIS Fatigue scores for autosomal dominant patients were observed in the Phase 1 trial that was recently completed in RYR1-RM patients. Furthermore, the PROMIS Physical Function (PROMIS-PF) will be used as a measure of physical functioning, upper-extremity function, and mobility. RYR1-RM participants will also use a diary to capture their symptoms. Lastly, the Syde® device will be used in this study to objectively assess activity levels in ambulatory participants with *RYR1*-RM.

Template No.: RWI\_TP\_EPI0011 Revision 2 Reference: RWI\_WI\_EPI0005

ARMGO Pharma, Inc. RYR1-RM Study Version 4.0 dated 10-SEP -2024 Protocol/Study No.: CL-EPI-001

Page 20 of 64

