Data will be extracted from the participants' medical records (both paper and/or electronic) at the Screening Visit (at site) and entered in an electronic case report form (eCRF). This data will be used to capture the participant's full medical history (starting from the earliest record available), including the date of *RYR1*-RM diagnosis, comorbidities, and medication use. Medical records may also be used to assess other clinical characteristics, including vital signs, forced vital capacity (FVC) and electrocardiogram (ECG) (if available in the participants' medical records within 12 months prior to the Screening Visit).

Data collected at study visits will be manually entered into the eCRF. The following data will be collected from participants at relevant time points for study assessments and procedures:

- Medical history (including biopsy details, if performed);
- Medication use (including all current and prior medications to treat symptoms of *RYR1*-RM);
- Full physical, neurological, and functional examination;
- Vital signs (heart rate, blood pressure, respiratory rate, temperature), FVC sitting and supine, and ECG;
- Strength measurements by QMA (shoulder abduction, elbow flexion and extension, knee flexion and extension), MMT (neck flexion), and HHD (neck flexion);
- 10 Meter Walk Test;
- 1-Minute Sit-to-Stand:
- Stair Climb Test; and
- PROMIS Fatigue, PROMIS-PF, IPAQ, and symptom diary.

Participants will be given periods of rest in between tests to reduce their burden. Ideally, all visits should be conducted in the morning to minimise the impact of the participant's daily activities on their energy levels, cognitive function, and mood. However, the actual timing of the visits may vary according to the capacity of the sites.

For details on data collected at each visit refer to the data collection schedule table in Section 4.5.

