#### a) PROMIS Fatigue, PROMIS-PF, and IPAQ questionnaires

PROMIS Fatigue (PROMIS-F): The PROMIS-F tool is a National Institutes of Health (NIH) developed Patient Reported Outcomes Measurement Information System (PROMIS) used to measure fatigue across a wide range of chronic health conditions. It has been used extensively and clinically validated across diverse chronic disorders. (39, 40). It can be administered as a Computerised Adaptive Test (CAT) or in various fixed length short forms. The PROMIS Short Form v1.0 Fatigue 7a (PROMIS F-SF 7a) is a reliable and valid 7-item questionnaire which has been evaluated across various populations, and it will be used to assess fatigue in this study (see Appendix 11.2). (41, 42) Using this measure, the participant is expected to respond to questions on symptoms over a period of 7 days prior to administration of the form. Each question has five response options ranging in value from one to five. Scores are represented as 'Never'-1, 'Rarely'-2, 'Sometimes'-3, 'Often'-4, and 'Always'-5. A total raw score for the short form with all questions answered is a sum of the values of the response to each question. The lowest possible raw score is 7; the highest possible raw score is 35. Using a score conversion table provided in the user manual, raw scores are translated into a T-score for each participant. The T-score rescales the raw score into a standardized score with a mean of 50 and a standard deviation (SD) of 10. (42) Higher PROMIS T-scores indicate higher fatigue. A PROMIS T-

Template No.: RWI\_TP\_EPI0011 Revision 2 Reference: RWI\_WI\_EPI0005

ARMGO Pharma, Inc. RYR1-RM Study Version 4.0 dated 10-SEP -2024 Protocol/Study No.: CL-EPI-001 Page 33 of 64

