# 4.5.2 Visit 1, Visit 2, and End of Study Visit

The following data will be collected for all enrolled participants at each follow-up time point:

- Medication use;
- Strength measurements using QMA, HHD, and MMT;
- 10-MWT;
- 1-Minute Sit-to-Stand Test;

Template No.: RWI\_TP\_EPI0011 Revision 2 Reference: RWI\_WI\_EPI0005

ARMGO Pharma, Inc. RYR1-RM Study Version 4.0 dated 10-SEP -2024 Protocol/Study No.: CL-EPI-001

Page 41 of 64

- 4SCT;
- PROMIS Questionnaires (at End of Study Visit only);
- IPAQ (at End of Study Visit only);
- Full physical, neurological, and functional examination (at End of Study Visit only);
- Syde® device removal (at Visit 1 only);
- Symptom Diary (to be completed daily between Screening Visit and End of Study Visit); and
- AE/SAE.

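### PROMIS and IPAQ are scheduled after all physical testing at Screening, with no binding position stated for End of Study, so same-day exertion may colour the answers

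*Protocol*

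**What the plan says.** Section 4.5.1 introduces the Screening activities as "listed in the order in which they will be collected during the visit". The order is consent; eligibility, which includes MMT, 10-MWT and FVC; records review; vital signs and ECG; QMA and HHD; 1-Minute Sit-to-Stand; 4SCT; the full examination; then the PROMIS questionnaires and IPAQ. The synopsis repeats the same list.

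Section 4.5.2 covers Visit 1, Visit 2 and End of Study in one list, introduced by "The following data will be collected for all enrolled participants at each follow-up time point". The forms, marked for End of Study only, stand after QMA, HHD, MMT, 10-MWT, sit-to-stand and 4SCT and before the full examination. Nothing in the section calls this list a sequence. The amendment table says of Section 4.5 that "The tests have been listed in the order in which they will be administered", which points towards a sequence but does not fix one in the current 4.5.2.

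On timing, Section 4.1 prefers morning visits "to minimise the impact of the participant's daily activities on their energy levels, cognitive function, and mood". It also plans rest between tests, without a stated duration.

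On the instruments, Section 2 states: "The PROMIS Fatigue scale will be used as a measure of fatigue severity in this study". For that form, Section 4.4.1.2 says that "the participant is expected to respond to questions on symptoms over a period of 7 days prior to administration of the form". IPAQ also covers the previous 7 days. The PROMIS-PF form in Appendix 11.3 has no recall window: its items ask about limitation or ability in the present.

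**The concern.** The secondary objective is the extent to which fatigue and physical function are affected, and the PROMIS results are T-scores read against a population mean of 50. The level of the score is therefore the result of interest.

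The protocol accepts in Section 4.1 that a participant's ordinary activity on the day can affect energy, cognition and mood. It then schedules the fatigue and function forms after a series of maximal-effort tests in people whose disease is marked by weakness and fatigue. If recent exertion colours the answers, the plausible direction is more reported fatigue and less reported function, so impairment would look somewhat greater than it is.

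Section 6.2.4.3 recognises self-report bias but relies on validated forms and on instructions to participants. It does not deal with when in the visit the forms are completed. Since every participant has the same order at Screening, a shift of this kind could not be separated from the true level in the analysis.

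**Working it through.** There is no figure in the plan to reproduce, because the sample size of up to 20 rests on feasibility. The check is of order, exposure and consequence.

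**1. Trials scheduled before the forms** (Section 4.4.1.1)

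| Test | Trials |
|---|---|
| QMA: 5 movements × 2 limbs × 3 | 30 |
| HHD neck flexion | 3 |
| MMT neck flexion | 3 |
| 10-MWT: 2 comfortable + 2 fast | 4 |
| 1-Minute Sit-to-Stand | 3 |
| 4SCT | 3 |
| Total | 46 |

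Without the two comfortable-speed walks the total is 46 − 2 = 44. The muscle testing in Appendix 11.1 is additional.

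**2. Position of the forms at the two visits**

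| | Screening (4.5.1) | End of Study (4.5.2, if read as a sequence) |
|---|---|---|
| 46 trials above | before the forms | before the forms |
| Full examination | before the forms | after the forms |
| Stated to be a sequence | yes | no |

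The only listed difference is the examination. If 4.5.2 is not a sequence, the End of Study position is simply left open.

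**3. Consequence for level and change.** Let b be the shift in a score due to the 46 trials and x the shift due to the examination. Assume that both are additive and that b is the same at both visits. With true means μS and μE and the listed orders:

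- Screening mean = μS + b + x
- End of Study mean = μE + b
- Change = (μE + b) − (μS + b + x) = (μE − μS) − x

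The level carries b + x at Screening and b at End of Study. In the change, b cancels and only x remains. The documents give no value for b or x, and either may be zero.

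**4. Exposure by instrument.** PROMIS-PF is the most exposed: its items are in the present tense and cover stairs, bending and vigorous activity, shortly after stair climbs and sit-to-stands. PROMIS Fatigue asks how often symptoms occurred over 7 days, so current state can act only by colouring recall. IPAQ asks for days and minutes of past activity and is the least exposed.

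**The case against.** The strongest reply is that the protocol does not contradict itself on the Screening position, that PROMIS Fatigue and IPAQ look back over 7 days, that rest is planned, and that these are secondary, descriptive endpoints in at most 20 people. All of that is true. It limits the importance of the point, but it does not supply a reason for placing the forms last, and the 7-day argument does not cover PROMIS-PF.

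A reader might infer more than the text supports:

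- *That the different position creates a spurious change between visits.* Section 4.5.2 pools three visits, mixes items specific to one visit with a daily diary, and is not called a sequence. Even read as one, it places the same 46 trials before the forms as at Screening. Only the examination moves, and apart from its muscle testing that is largely observation.
- *That exertion demonstrably raises the fatigue scores.* No passage shows this. It is a plausible risk.
- *That the forms follow about an hour of exertion.* Section 4.5 gives about 90 minutes for the whole Screening Visit, including consent, records review, questionnaires and device fitting. The time spent in exertion is not stated, and MMT and 10-MWT come at the start.
- *That the bias can be sized.* A shift of, say, 2 to 3 T-score points has no source in the documents, and expressing it in standard errors would only restate the guess.

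**Conclusion.** The point stands in a limited form. At Screening the protocol explicitly puts PROMIS and IPAQ after all strength and functional testing and the examination. At End of Study it lists them after the same tests without fixing an order. Same-day exertion may influence the answers, chiefly on PROMIS-PF, to a lesser degree on PROMIS Fatigue, and least on IPAQ.

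What is at risk is the level read against T = 50, by an amount that cannot be derived from the documents. The Screening-to-End-of-Study change is exposed only through the listed position of the full examination. That conclusion assumes that 4.5.2 is followed in its listed order and that the effect of the main tests is the same at both visits.

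Importance is minor to moderate, because the endpoints are secondary and descriptive. Confidence is moderate: the order is plain in the text, but the carry-over is not demonstrated.

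**What to change.** In Sections 4.5.1 and 4.5.2 and in the synopsis, move PROMIS Fatigue, PROMIS-PF with its added single item, and IPAQ ahead of every physical test: directly after consent at Screening, and as the first activity at End of Study. State that this order is binding at both visits.

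The change reorders existing lists and adds no procedure. Its cost is an amendment, plus completed forms from some participants who then prove ineligible. If any participant has already been screened under the present order, record which order applied at each visit so that their change scores can be read accordingly.

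The same edit should reconcile two other points on order at Screening. Section 4.4.1.1 puts QMA and HHD before MMT and 10-MWT, whereas 4.5.1 has MMT and 10-MWT first. Section 5 has the Syde device fitted before the stair climb, whereas 4.5.1 lists fitting after it.
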